9.3.3. Secondary Endpoints Analysis

9.3.3.1. Multiplicity Adjusted Endpoints

A graphical approach will be used to control the overall Type I error for the primary objective and testing the superiority of LY3209590 compared with insulin degludec for

- change in HbA1c from baseline to Week 26 (Visit 22)
- time in normal glucose range between 70 and 180 mg/dL (3.9 and 10.0 mmol/L) inclusive, measured by CGM 4 weeks prior to Week 26 (Visit 22), and
- event rate of participant-reported clinically significant nocturnal hypoglycemia (<54 mg/dL [3.0 mmol/L] or severe) during treatment phase up to Week 52 (Visit 29).

The superiority test in change from baseline to Week 26 (Visit 22) in HbA1c will be based on the same primary endpoint analysis methods as described above.

The rate of nocturnal hypoglycemia will be analyzed by a negative binomial regression with treatment, baseline HbA1c, baseline incidence of nocturnal hypoglycemia, and carbohydrate counting for prandial insulin dosing (yes/no) as independent variables, and log (exposure in year) as the offset.

The time in glucose range between 70 and 180 mg/dL (3.9 and 10.0 mmol/L) inclusive measured by CGM will be analyzed using an ANCOVA model for treatment regimen estimand (using data from EAS1) and an MMRM model for efficacy estimand (using data from EAS2).

In the ANCOVA model, treatment, strata (country, baseline HbA1c stratum [$<8.0\%$, $\geq 8.0\%$]), CGM use prior to study entry [yes/no], and carbohydrate counting for prandial insulin dosing [yes/no]), and baseline of the dependent variable will be used.

The MMRM model will include treatment, strata (country, baseline HbA1c stratum [$<8.0\%$, $\geq 8.0\%$]), CGM use prior to study entry [yes/no], and carbohydrate counting for prandial insulin dosing [yes/no]), visit and treatment-by-visit interaction as fixed effects, and baseline of the dependent variable as a covariate.

For treatment regimen estimand, the missing data will be imputed by multiple imputation with the approach similar to the imputation used for the primary endpoint.

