1.2. Study Design

- Study BDCY is a Phase 3, open-label, 2-arm, parallel-design, randomized control study to investigate if LY3209590 is noninferior to insulin degludec in adult participants with T1D who are treated with basal-bolus insulin MDI therapy.
- This study consists of a 1-week screening period, a 2-week lead-in period, a 52-week treatment period, and a 5-week safety follow-up period.
- Participants will be randomly assigned in a 1:1 ratio to LY3209590:insulin degludec. All participants will be treated with basal-bolus MDI therapy, which will be titrated to glycemic targets and as clinically indicated for hyperglycemia.
- Participants will be stratified based on country, HbA1c stratum (<8% and \geq 8%) at screening Visit 1, CGM use prior to study entry (yes/no), and carbohydrate counting for prandial insulin dosing (yes/no).
- Rescue therapy will be considered during the treatment period if the participants meet the protocol criteria of severe, persistent hyperglycemia.
- If study intervention is permanently discontinued, the participant will be encouraged to continue participation in the study for continued monitoring. Both efficacy (including HbA1c) and safety data will continue to be collected per the schedule of activities in the protocol.

2. Statistical Hypotheses

The primary objective of this study is to test the hypothesis that LY3209590 is noninferior to insulin degludec on glycemic control as measured by change in HbA1c from baseline to Week 26 (Visit 22) in adults with T1D currently on basal-bolus insulin MDI therapy.

The null hypothesis ($H_{1,0}$) is the difference between LY3209590 and insulin degludec in the change in HbA1c from baseline to Week 26 (Visit 22) is greater than the noninferiority margin (NIM).

The NIMs of 0.4% and 0.3% will both be tested to meet different regulatory requirements. A 2-sided 95% confidence interval (CI) will be used for testing noninferiority.

Secondary hypotheses

The key secondary (multiplicity adjusted) objectives are to test the hypotheses that LY3209590 is superior to insulin degludec with respect to

- change in HbA1c from baseline to Week 26 (Visit 22)
 - $H_{2,0}$: the difference (LY3209590 - insulin degludec) ≥ 0.0
- time in glucose range between 70 and 180 mg/dL (3.9 and 10.0 mmol/L), inclusive, measured by CGM 4 weeks prior to Week 26 (Visit 22)
 - $H_{3,0}$: the difference (LY3209590 - insulin degludec) ≤ 0.0 , and

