Event rate of Level 2 hypoglycemia events (events/participant/year) • all documented	Baseline, Weeks 0-6, 0-12, 0-26, 0-52, 12-26, 26-52, and the posttreatment period	Negative binomial regression with treatment, baseline HbA1c, and baseline Level 2 hypoglycemia rate as covariates and log (exposure/365.25 days) as the offset in the model
Event rate of Level 3 hypoglycemia events (events/participant/100 years) • all documented	Baseline, Weeks 0-26, 0-52, 26-52, and the posttreatment period	Negative binomial regression with treatment and baseline HbA1c, and baseline Level 3 hypoglycemia rate as covariates and log (exposure/36525 days) as the offset in the model If the number of events is too small to run the negative binomial regression, the exposure-adjusted rate (calculated by total number of events divided by total exposure for individual participants) will be provided, and the empirical method (see Appendix 10 [Section 6.10] for details) will be used for treatment comparison.
Event rate of Level 2/3 hypoglycemia events (events/participant/year) • all documented • nocturnal, and • non-nocturnal	Baseline, Weeks 0-6, 0-12, 0-26, 0-52, 12-26, 26-52, and the posttreatment period	A negative binomial regression with treatment, baseline HbA1c, and baseline hypoglycemia rate of the same hypoglycemia type as covariates and log (exposure/365.25 days) as the offset in the model. The plots of the mean cumulative functions (MCFs) by each treatment arm will also be created. The population mean for cumulative number of events up to time t, M(t), will be estimated using a nonparametric estimation method described by Nelson ^b .
Incidence of Level 1 hypoglycemia events • all documented	Baseline, Weeks 0-6, 0-12, 0-26, 0-52, 12-26, 26-52, and the posttreatment period	Logistic regression with treatment, baseline HbA1c, and baseline Level 1 hypoglycemia incidence as covariates
Incidence of Level 2 hypoglycemia events • all documented	Baseline, Weeks 0-6, 0-12, 0-26, 0-52, 12-26, 26-52, and the posttreatment period	Logistic regression with treatment, baseline HbA1c, and baseline Level 2 hypoglycemia incidence as covariates
Incidence of Level 3 hypoglycemia events • all documented	Baseline, Weeks 0-26, 0-52, 26-52, and the posttreatment period	Logistic regression with treatment and baseline HbA1c as covariates

Endpoint	Analysis Period ^a	Statistical Method

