Incidence of Level 2/3 hypoglycemia events 
 • all documented • nocturnal, and • non-nocturnal 	Baseline, Weeks 0-6, 0-12, 0-26, 0-52, 12-26, 26-52, and the posttreatment period	Logistic regression with treatment, baseline HbA1c, and baseline hypoglycemia incidence of the same hypoglycemia type as covariates.
Potential persistent-recurrent hypoglycemia events 
 • identified by investigators and • identified by a prespecified criteria (defined in Appendix 9 [Section 6.9]) 	Safety analysis period (see the definition in Section 4.6)	The number of participants with at least 1 event will be summarized and compared by Fisher's exact test. The number of events will also be provided. Listings of the events will also be provided.

Abbreviations: HbA1c = hemoglobin A1c; Level 2/3= Level 2 and Level 3 composite; mITT = modified intent-to-treat.

^a For analysis for baseline period, negative binomial regression or logistic regression will not include baseline HbA1c and baseline hypoglycemia for treatment companions.

b (Nelson 2003)

Note: The yearly hypoglycemia rate during the defined period is calculated by the number of hypoglycemic events within the period/number of days a participant is at risk within the period \times 365.25. For rare events, 100-year rate will be provided. The hypoglycemia incidence during the defined period indicates if the participant has at least 1 hypoglycemia event within the period (yes/no).

4.6.3.1.1.1. Sensitivity AnalysisError! No document variable supplied.

A sensitivity analysis will be done for selected hypoglycemic endpoints where all hypoglycemic events are considered 1 hypoglycemic episode until a succeeding glucose value is ≥ 70 mg/dL.

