Incidence of Level 2 hypoglycemic events: • 24-hour	Baseline, 4 weeks prior to Weeks 4, 8, 12, 16, 26, 36, 40, 44, 48, and 52, 6 weeks prior to Weeks 22 and 32, 0-12, 12-26, 26-52, 0-26, 0-52, posttreatment period.	Logistic regression with treatment, baseline HbA1c and baseline Level 2 hypoglycemia incidence as covariates.
Incidence of Level 2 hypoglycemic events ending with ≥ 70 mg/dL: • 24-hour	Baseline, 4 weeks prior to Weeks 4, 8, 12, 16, 26, 36, 40, 44, 48, and 52, 6 weeks prior to Weeks 22 and 32, 0-12, 12-26, 26-52, 0-26, 0-52, posttreatment period.	Logistic regression with treatment, baseline HbA1c and baseline incidence for Level 2 hypoglycemia ending with ≥ 70 mg/dL as covariates.
Duration of Level 1 or Level 2 hypoglycemic events: • 24-hour	4 weeks prior to Weeks 4, 8, 12, 16, 26, 36, 40, 44, 48, and 52, 6 weeks prior to Weeks 22 and 32, 0-12, 12-26, 26-52. 0-26 and 0-52. Baseline and post-treatment period	MMRM model will include treatment, strata (country, CGM use prior to study entry [yes/no], and carbohydrate counting for prandial insulin dosing [yes/no], baseline HbA1c stratum), time and treatment-by-time interaction as fixed effects, and baseline duration as a covariate. For each timepoint, ANCOVA model with treatment, strata (country, CGM use prior to study entry [yes/no], and carbohydrate counting for prandial insulin dosing [yes/no], baseline HbA1c stratum) as fixed effects, and baseline duration as a covariate. ANOVA models only include treatment.

Endpoint	CGM Period	Statistical Method
Duration of Level 2 hypoglycemic events: • 24-hour	Baseline, 4 weeks prior to Weeks 4, 8, 12, 16, 26, 36, 40, 44, 48, and 52, 6 weeks prior to Weeks 22 and 32, 0-12, 12-26, 26-52, 0-26, 0-52, posttreatment period.	Same models as for Level 1 or Level 2 hypoglycemic events. A listing will be provided for participants with Level 2 hypoglycemia episodes lasting >360 minutes
Duration of Level 2 hypoglycemic events ending with $BG \geq 70$ mg/dL: • 24-hour	Baseline, 4 weeks prior to Weeks 4, 8, 12, 16, 26, 36, 40, 44, 48, and 52, 6 weeks prior to Weeks 22 and 32, 0-12, 12-26, 26-52, 0-26, 0-52, posttreatment period.	Same models as for Level 1 or Level 2 hypoglycemic events.

Abbreviations: ANOVA = analysis of variance; ANCOVA = analysis of covariance; CGM = Continuous Glucose monitor; HbA1c = hemoglobin A1c; MMRM = mixed model for repeated measures.

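### The alpha-controlled nocturnal hypoglycemia rate model leaves out country and prior CGM use, both randomisation factors, and may give up a little precision

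*SAP*

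**What the plan says.** SAP 1.2 lists four randomisation factors: "Participants will be stratified based on country, HbA1c stratum" at screening, then "CGM use prior to study entry (yes/no), and carbohydrate counting for prandial insulin dosing (yes/no". Protocol 6.3 gives the same four.

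The event rate of clinically significant nocturnal hypoglycemia up to Week 52 is one of three key secondary endpoints in the graphical testing procedure (SAP 2.1, 4.4.1). Protocol 9.3.3.1 specifies a "negative binomial regression with treatment, baseline HbA1c, baseline incidence of nocturnal hypoglycemia". It adds a term for carbohydrate counting and uses log exposure as the offset. SAP 4.4.1.2 sends this endpoint to 4.6.3.1.1, where the Level 2/3 row reads "A negative binomial regression with treatment, baseline HbA1c, and baseline hypoglycemia rate of the same hypoglycemia type as covariates", with log exposure as the offset. That row covers all-documented, nocturnal and non-nocturnal events.

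Other models are fuller. For the duration of CGM-derived hypoglycemia, SAP 4.6.3.1.2 states "MMRM model will include treatment, strata (country, CGM use prior to study entry [yes/no" and goes on to carbohydrate counting and the HbA1c stratum. SAP 4.9 declares no change from the protocol's analyses.

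**The concern.** A factor used to balance the arms is normally also used in the analysis. If it predicts the outcome and is left out, its contribution stays in the residual variation, and the standard error is larger than the design requires.

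Both missing factors could plausibly matter here. The endpoint depends on meter checks and diary entries, prompted by symptoms or CGM readings below 70 mg/dL (protocol 8.1.1.1; SAP 4.4.1.1). Local practice and earlier CGM experience may affect how many events are recorded. SAP 4.7.2.2 itself examines hypoglycemia rates by region and by prior CGM use, but no reason is given for keeping these factors out of the main test.

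At stake is some power for an alpha-controlled endpoint and for the all-documented Level 2/3 rate, which is an other secondary endpoint. The main model should also be the same in both documents.

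**Working it through.** **1. Models side by side**

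| Model | Country | Prior CGM use | Carbohydrate counting | HbA1c |
|---|---|---|---|---|
| Nocturnal Level 2/3 rate, protocol 9.3.3.1 | no | no | yes | baseline value |
| Nocturnal Level 2/3 rate, SAP 4.6.3.1.1 | no | no | no | baseline value |
| HbA1c change, SAP 4.3.2 | yes | yes | yes | baseline value |
| Time in range, SAP 4.4.1.2 | yes | yes | yes | stratum |
| SF-36 and EQ-5D ANCOVA, SAP 4.4.2.3.2 and 4.4.2.3.3 | yes | yes | yes | stratum |
| Duration of CGM hypoglycemia, SAP 4.6.3.1.2 | yes | yes | yes | stratum |
| HbA1c <7% with no nocturnal Level 2 event, SAP 4.5.1 | yes | yes | yes | baseline value |

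So a tertiary composite that contains nocturnal hypoglycemia is adjusted for country and prior CGM use, while the alpha-controlled nocturnal rate is not.

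**2. The plan's power figure**

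Inputs (protocol 9.5, SAP 5): rates m1 = 3.37 and m0 = 4.87 per participant-year, SD 7.13 in each arm, 284 completers per arm, alpha 0.05 taken as two-sided, stated power 80%. One year of exposure is assumed.

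- Dispersion: k = (SD² − m)/m², giving k1 = 4.18, k0 = 1.94, and 2.75 at the mean rate.
- Var(log RR) = [1/m1 + 1/m0 + k1 + k0]/284.
- log(4.87/3.37) = 0.368.

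| Dispersion used | SE | Power |
|---|---|---|
| Arm-specific, 4.18 and 1.94 | √(6.62/284) = 0.153 | 67.4% |
| 2.75 in both arms | √(6.01/284) = 0.145 | 71.6% |
| 1.94 in both arms | √(4.38/284) = 0.124 | 84.3% |

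A common k of 2.20 gives 80%. The dispersion behind the stated figure is not given, so that figure is neither reproduced nor called wrong. It names no covariates and does not settle the point either way.

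**3. Analytic range, with no baseline hypoglycemia in the model**

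The documents give no effect sizes for country or prior CGM use. Assumed ranges: between-country SD of the log rate s from 0 to 0.4; rate ratio for prior CGM use r from 1.0 to 1.5, with half the participants prior users.

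Residual dispersion: 1 + k_res = (1 + k)/[exp(s²) × (0.5r² + 0.5)/(0.5r + 0.5)²].

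Strongest case, s = 0.4 and r = 1.5: divisor = 1.174 × 1.040 = 1.220.

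- k = 1.94: k_res = 2.938/1.220 − 1 = 1.41. SE ratio 0.870; power 84.3% to 92.6%.
- k = 2.75: k_res = 3.752/1.220 − 1 = 2.07. SE ratio 0.880; power 71.6% to 82.0%.

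Weakest case, s = 0 and r = 1: ratio 1.000.

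**4. Simulation**

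Settings: 200 trials per scenario, 8 equal countries, half prior CGM users, stratified 1:1 allocation. The rate model was fitted with and without country and prior CGM use.

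| s, r | Two-week baseline count in model | SE without | SE with | Ratio |
|---|---|---|---|---|
| 0, 1.0 | yes | 0.1154 | 0.1156 | 1.002 |
| 0.2, 1.25 | yes | 0.1137 | 0.1131 | 0.995 |
| 0.4, 1.5 | yes | 0.1087 | 0.1051 | 0.967 |
| 0.4, 1.5 | no | 0.1169 | 0.1118 | 0.956 |

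Even without the baseline count, the simulated gain in the strongest case is about 4%, well short of the analytic 13%.

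**5. In power points**

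Applying the first three ratios to the arm-specific case (0.368/0.153 = 2.412):

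- 2.412/1.002 − 1.960 = 0.447, power 67.2%
- 2.412/0.995 − 1.960 = 0.464, power 67.9%
- 2.412/0.967 − 1.960 = 0.534, power 70.3%

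Against 67.4%, the change runs from nil to about 3 points. From the 84.3% starting point, the 0.967 ratio gives 2.965/0.967 − 1.960 = 1.106, or 86.6%. Carbohydrate counting was not part of these calculations.

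**The case against.** The strongest defence is that this is a consistent choice for a safety measure. SAP 1.1 calls the nocturnal rate a safety measure, and the general safety MMRM and ANCOVA models in SAP 4.6, used for body weight among others, carry no strata. Nor do all other comparisons adjust: the treatment-satisfaction and basal-insulin-experience items use Wilcoxon tests. This stands against any claim that hypoglycemia is the only exception. It does not explain why an alpha-controlled superiority test should follow the descriptive safety convention.

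A second defence is that the baseline rate already absorbs recording habits, because all participants use the study meter, diary and CGM in the lead-in. That stands in part, and it is why the simulated gain is small. It is not complete. Visit 3 falls 11 to 17 days after the diary is dispensed. At 4.87 events a year that is 4.87 × 11/365.25 = 0.15 to 4.87 × 17/365.25 = 0.23 expected events, so most participants would probably show none.

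Some stronger readings are tempting but unsupported:

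- **That power would rise from 67% to as much as 76%.** This requires the two factors to explain 20% of the raw dispersion. That share is pure assumption, and it ignores the covariates already in the model.
- **That the incidence analyses lose precision too.** The SAP uses "Logistic regression with treatment, baseline HbA1c, and baseline hypoglycemia incidence of the same hypoglycemia type as covariates", but adding strata to a logistic model raised the SE of the log odds ratio in the strongest simulated case (0.1862 to 0.1900), while the estimate moved from −0.285 to −0.296.
- **That both documents omit the factors from every hypoglycemia model.** The protocol names no incidence covariates (9.3.5), and SAP 4.7.2.2 enters prior CGM use and region in subgroup interaction models for these rates. Those are not the main test.

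**Conclusion.** The point holds for the main nocturnal Level 2/3 rate model. Country and prior CGM use are absent from it in both documents, and carbohydrate counting is absent from the SAP version only.

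A reader might infer a biased test or an inflated type 1 error. The documents do not support that: leaving out balanced strata usually makes the test conservative, so any cost is lost precision.

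That cost is modest and uncertain. It ranges from none to about a 3% smaller SE (about 0 to 3 power points) with baseline hypoglycemia in the model, and up to about 13% in the strongest analytic case without it. Both ranges rest on assumed effects of country and prior CGM use. If the factors are not prognostic, adjusting costs almost nothing (SE ratio 1.002). The change is worth making because it is cheap and concerns an alpha-controlled endpoint.

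**What to change.** Before database lock:

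- Add country, prior CGM use and carbohydrate counting to the negative binomial models for the nocturnal and all-documented Level 2/3 rates over Weeks 0-52.
- Prespecify how small countries are pooled to region, and a fallback for non-convergence that drops country first.
- State in SAP 4.9 the covariate set adopted and how it differs from protocol 9.3.3.1. Include whether baseline hypoglycemia enters as incidence (protocol) or rate (SAP).

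Level 3 models may keep the shorter list because events are few. No change to the logistic incidence models is requested on grounds of precision.

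The cost is SAP wording and three variables already collected for randomisation. The small downside is the pooling and fallback rule, which must be fixed in advance so that the model for an alpha-controlled test is not chosen after seeing the data.

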4.6.3.1.2. Hypoglycemic Events derived from CGM

Level 2, Level 2 ending with BG value ≥ 70 mg/dL, and Level 1 or Level 2 hypoglycemic events collected from the sponsor provided CGM are defined in Appendix 6, Section 6.6.2. The analysis for incidence, event rate, and duration are described in the table below. All data are included in the analysis. Missing data will be handled as described in Appendix 6.

Endpoint	CGM Period	Statistical Method
Event rate of Level 1 or Level 2 hypoglycemic events (events/participant/year): 
 • 24-hour 	Baseline, 4 weeks prior to Weeks 4, 8, 12, 16, 26, 36, 40, 44, 48, and 52, 6 weeks prior to Weeks 22 and 32, 0-12, 12-26, 26-52, 0-26, 0-52, posttreatment period	Negative binomial regression with treatment, baseline HbA1c and baseline Level 1 or Level 2 hypoglycemia rate as covariates, log (exposure/365.25 days) as the offset in the model.
Event rate of Level 2 hypoglycemic events (events/participant/year): 
 • 24-hour 	Baseline, 4 weeks prior to Weeks 4, 8, 12, 16, 26, 36, 40, 44, 48, and 52, 6 weeks prior to Weeks 22 and 32, 0-12, 12-26, 26-52, 0-26, 0-52, posttreatment period	Negative binomial regression with treatment, baseline HbA1c and baseline Level 2 hypoglycemia rate as covariates, log (exposure/365.25 days) as the offset in the model.

Endpoint	CGM Period	Statistical Method
Event rate of Level 2 hypoglycemic events ending with ≥ 70 mg/dL (events/participant/year): • 24-hour	Baseline, 4 weeks prior to Weeks 4, 8, 12, 16, 26, 36, 40, 44, 48, and 52, 6 weeks prior to Weeks 22 and 32, 0-12, 12-26, 26-52, 0-26, 0-52, posttreatment period.	Negative binomial regression with treatment, baseline HbA1c and baseline rate for Level 2 hypoglycemia ending with ≥ 70 mg/dL as covariates, log (exposure/365.25 days) as the offset in the model.
Incidence of Level 1 or Level 2 hypoglycemic events: • 24-hour	Baseline, 4 weeks prior to Weeks 4, 8, 12, 16, 26, 36, 40, 44, 48, and 52, 6 weeks prior to Weeks 22 and 32, 0-12, 12-26, 26-52, 0-26, 0-52, posttreatment period.	Logistic regression with treatment, baseline HbA1c and baseline Level 1 or Level 2 hypoglycemia incidence as covariates. The total number of episodes, number of episodes that includes Level 2 hypoglycemia episodes, and number of episodes that include glucose readings <54 mg/dL (3.0 mmol/L) but no Level 2 hypoglycemia episodes will be summarized for each CGM period.
Incidence of Level 2 hypoglycemic events: • 24-hour	Baseline, 4 weeks prior to Weeks 4, 8, 12, 16, 26, 36, 40, 44, 48, and 52, 6 weeks prior to Weeks 22 and 32, 0-12, 12-26, 26-52, 0-26, 0-52, posttreatment period.	Logistic regression with treatment, baseline HbA1c and baseline Level 2 hypoglycemia incidence as covariates.
Incidence of Level 2 hypoglycemic events ending with ≥ 70 mg/dL: • 24-hour	Baseline, 4 weeks prior to Weeks 4, 8, 12, 16, 26, 36, 40, 44, 48, and 52, 6 weeks prior to Weeks 22 and 32, 0-12, 12-26, 26-52, 0-26, 0-52, posttreatment period.	Logistic regression with treatment, baseline HbA1c and baseline incidence for Level 2 hypoglycemia ending with ≥ 70 mg/dL as covariates.
Duration of Level 1 or Level 2 hypoglycemic events: • 24-hour	4 weeks prior to Weeks 4, 8, 12, 16, 26, 36, 40, 44, 48, and 52, 6 weeks prior to Weeks 22 and 32, 0-12, 12-26, 26-52. 0-26 and 0-52. Baseline and post-treatment period	MMRM model will include treatment, strata (country, CGM use prior to study entry [yes/no], and carbohydrate counting for prandial insulin dosing [yes/no], baseline HbA1c stratum), time and treatment-by-time interaction as fixed effects, and baseline duration as a covariate. For each timepoint, ANCOVA model with treatment, strata (country, CGM use prior to study entry [yes/no], and carbohydrate counting for prandial insulin dosing [yes/no], baseline HbA1c stratum) as fixed effects, and baseline duration as a covariate. ANOVA models only include treatment.

Endpoint	CGM Period	Statistical Method
Duration of Level 2 hypoglycemic events: • 24-hour	Baseline, 4 weeks prior to Weeks 4, 8, 12, 16, 26, 36, 40, 44, 48, and 52, 6 weeks prior to Weeks 22 and 32, 0-12, 12-26, 26-52, 0-26, 0-52, posttreatment period.	Same models as for Level 1 or Level 2 hypoglycemic events. A listing will be provided for participants with Level 2 hypoglycemia episodes lasting >360 minutes
Duration of Level 2 hypoglycemic events ending with $BG \geq 70$ mg/dL: • 24-hour	Baseline, 4 weeks prior to Weeks 4, 8, 12, 16, 26, 36, 40, 44, 48, and 52, 6 weeks prior to Weeks 22 and 32, 0-12, 12-26, 26-52, 0-26, 0-52, posttreatment period.	Same models as for Level 1 or Level 2 hypoglycemic events.

Abbreviations: ANOVA = analysis of variance; ANCOVA = analysis of covariance; CGM = Continuous Glucose monitor; HbA1c = hemoglobin A1c; MMRM = mixed model for repeated measures.

Note: The hypoglycemic rate during the defined period is calculated by the number of hypoglycemic events within the period/number of days the participant at risk within the period \times 365.25. The hypoglycemia incidence during the defined period indicates if the participant has at least 1 hypoglycemic event within the period (Yes/No).

